6.4 Recruitment and Informed Consent (Prospective Group Only)

Patients are typically on mechanical ventilation for approximately 3-5 days, allowing several days from the time of identification for recruitment and consent. Because patients will be sedated and intubated, informed consent will be obtained from the patients' legally authorized representatives (LAR). Specifically, a member of the patient's care team will give each family of mechanically ventilated patients a recruitment card (Appendix B) and explain that a member of the research team will be approaching them to discuss the study. This ensures that the LARs are introduced to the study by the patients' care team.

The LAR will sign the informed consent document prior to any procedures being done specifically for the study only (i.e. above routine care). A copy of the signed informed consent document will be given to the LAR for their records, with a copy placed in the patient's medical record. Because patients may remain sedated following extubation, it may be not practicable to re-consent all patients following extubation. Patients in the Intensive Care Unit are assessed for confusion/delirium as standard of care using the Confusion Assessment Method for the ICU (CAM-ICU). Therefore, each patient's routine CAM-ICU score will be reviewed daily by a member of the study team. Those with negative CAM-ICU scores will be informed by a member of the study team that they were enrolled in a research study by their LAR, and the patient will be provided the opportunity determine whether they wish to remain enrolled in the study using the regained capacity portion of the consent form (Appendix C). Patients with positive CAM-ICU scores or who are transferred outside of the ICU (where CAM-ICU is not conducted) will not be re-consented. It is important to note that at this time all study interventions would have been completed; patient consent can only be obtained for continued data collection. Patients who do not wish to continue will be treated as outlined in [Section 6.6](#).

All informed consent procedures (initial and in the event of regained capacity) will be obtained and documented on an IRB-approved informed consent form (Appendix C) in accordance with the OhioHealth Research Institute (OHRI) policy for obtaining and documented informed consent.

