6.5 Study Treatment/Interventions (Prospective Group Only)

6.5.1 Standard of Care Extubation Readiness Assessments

As standard of care, mechanically ventilated patients are reviewed daily for extubation readiness. Extubation readiness is indicated if all of the following are true: 1. The cause of respiratory failure has improved; 2. The patient can protect his or her airway; 3. Mental status is awake and alert or easily aroused; 4. Cough/secretions are appropriately managed. This standard of care extubation readiness process will occur for all patients, regardless of whether or not they are enrolled in the research study.

Once the above criteria are met, patients undergo daily spontaneous breathing trials (SBT), where the patients are observed for approximately 30-120 minutes with reduced sedation and ventilator support.

Patients that do well with minimal ventilator support during this time can generally be scheduled for extubation. All SBTs will be conducted as outlined in Appendix D.

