6.5.2.2 Study Standardized, Intermittent NIV/HFNC Protocol

Patients that **do** meet all study eligibility criteria will be placed in the standardized, intermittent NIV/HFNC protocol as outlined below. For NIV, OhioHealth Grant Medical Center routinely utilizes BiPAP, a non-invasive ventilator. For HFNC, OhioHealth Grant Medical Center utilizes a heated high flow generator, an oxygen blender, and a humidifier. Please see Appendix D for BiPAP/HFNC setup, monitoring, and clinical decision making guide and Appendix E for device specification sheets.

Briefly, over the 24-hour-period following extubation, enrolled patients will receive BiPAP for 2-hour intervals (e.g., 2 hours on, 2 hours off) during the day and continuously at night. During BiPAP breaks, patients will receive heated high flow nasal cannula (HFNC) oxygen. As such, the intervention portion of this study is limited to approximately 24 hours (the 24-hour-period following extubation).

- The treating physician or advanced practice provider will order the BIPAP settings and care according to current standard methods.
- The Respiratory Therapy Team will set up, turn on and take off the BIPAP. They will also discuss the patient's care on BIPAP at the start of each shift with the RN and monitor the BIPAP approximately every 3 hours.
- The registered nurse (RN)/respiratory therapist (RT) team is responsible for the routine care they provide these patients, including assessing and monitoring the patient while they are on BIPAP for the study. They will identify, document and inform the physician and RT if problems and/or escalation of patient care occur.

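### Section 6.4 takes the intervention to be over whenever a patient regains capacity and limits consent to data collection, but nothing in the protocol ensures that timing

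*Combined protocol and SAP*

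**What the plan says.** Section 6.4 explains that patients are sedated and intubated at recruitment, so the LAR consents. It allows that some patients may still be sedated after extubation and that re-consenting everyone may not be feasible. It then sets a rule for recovered capacity: "each patient's routine CAM-ICU score will be reviewed daily by a member of the study team", and a negative score leads to the patient being informed of the enrolment and asked whether to stay in, using the regained-capacity part of the consent form (Appendix C). Patients with a positive score, or who have left the ICU, are not re-consented. The section adds that "at this time all study interventions would have been completed; patient consent can only be obtained for continued data collection", and it refers patients who do not wish to continue to Section 6.6.

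Three other places bear on the timing:

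- Section 6.5.1 lists among the readiness conditions for extubation: "Mental status is awake and alert or easily aroused". In the breathing trial that follows, patients are "observed for approximately 30-120 minutes with reduced sedation and ventilator support".
- Section 6.5.2.2 starts the intervention at extubation ("over the 24-hour-period following extubation, enrolled patients will receive BiPAP for 2-hour intervals") and states that "the intervention portion of this study is limited to approximately 24 hours".
- The study calendar in Section 6.7 marks the NIV/HFNC protocol on Study Day 0 and Study Day 1.

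**The concern.** The sentence in Section 6.4 is a categorical statement about timing, and the limit on what the patient may consent to rests on it. If the intervention has ended, only data collection is left to decide, and the limit is reasonable. If it has not ended, the limit removes from a patient with capacity the decision on the part of the study still being delivered.

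This is a participant-protection point. Section 8.1 attributes the only research-related physical risks to BiPAP and HFNC. The protocol rates those risks as mild, but they fall in the intervention hours, and those are the hours the sentence leaves outside the patient's decision. No endpoint, estimate or sample-size figure is affected.

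**Working it through.** The plan gives no figure to reproduce. The check is a comparison of timelines.

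**Inputs**

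| Item | Value | Source |
|---|---|---|
| Start of intervention | extubation (0 h) | Section 6.5.2.2 |
| End of intervention | about 24 h | Section 6.5.2.2; Days 0 and 1 in Section 6.7 |
| Interval between CAM-ICU reviews | daily, taken as 24 h | Section 6.4 |
| Delay before the first review | none stated | Section 6.4 |
| Trigger for approaching the patient | negative CAM-ICU, no time condition | Section 6.4 |
| Mental status at extubation | alert or easily roused | Section 6.5.1 |
| Planned prospective sample | 40 | Section 5 |
| Share CAM-ICU negative during the intervention | not given | none |

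**Step 1: does a review fall inside the intervention?** Reviews per intervention window = window length / review interval = 24 h / 24 h = 1. With no deferral, about one review per patient falls before the intervention ends. This is inferred from the word daily and the absence of a stated delay; the protocol does not say it outright.

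**Step 2: can that review be negative?** The protocol does not rule it out. Patients are extubated only when their mental status allows, after a trial with reduced sedation. Section 6.4 says only that patients may remain sedated, which leaves room for those who do not.

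**Step 3: when would the sentence hold for every patient?** Under either of two conditions: no patient is CAM-ICU negative at a review within the first 24 hours or so, or the review and re-consent begin only after the intervention ends. The documents state neither.

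**Step 4: how many patients?** Let p be the share with a negative score at a review during the intervention. The number affected is 40 × p. With p unknown, the bounds are 40 × 0 = 0 and 40 × 1 = 40.

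Two features would pull the number down. Section 6.3.2 uses daily for a report run Monday through Friday. If the CAM-ICU review followed the same working pattern, some patients extubated just before a weekend would have no review in the window. Patients who leave the ICU within the window are not re-consented at all. Neither feature makes p equal to 0.

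**The case against.** The strongest reply is that the phrase about timing describes when re-consent is meant to happen, so the sentence is a loosely worded intention. That reading is possible. It still leaves a gap, because no passage tells staff to wait until the intervention has ended, and the negative score is the only trigger given. The reply does show that deleting the sentence is not the only remedy; qualifying it would also serve.

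It is also fair to say that being awake is not the same as having capacity. CAM-ICU assesses confusion and delirium, and an easily roused patient may well score positive. That limits the point to some patients. It does not remove it, since Section 6.4 itself takes a negative score as the sign that the patient can be asked.

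Four stronger readings are tempting, and the documents do not support them:

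- **Sections 6.4 and 6.6 contradict each other.** They do not. Section 6.4 sends patients who decline to Section 6.6, which provides for withdrawal by the patient or the LAR. Section 6.4 also asks about staying in the study as such, which softens the limit.
- **Patients would be told that the intervention is finished while still receiving it.** The sentence is addressed to the reader of the protocol. What patients are told depends on Appendix C, which is not in the text reviewed and may already deal with this.
- **The analysis would suffer because a stop could be recorded as either a withdrawal or intolerance.** Section 6.6 treats both the same way: not replaced, and included in the intention-to-treat (ITT) analysis. Receipt of the protocol as directed depends on a minimum of 6 hours of BiPAP in 24 hours, whatever the reason for stopping.
- **A particular number of patients is affected.** No passage gives the share with a negative score in the first day, so any figure between the bounds would be a guess.

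**Conclusion.** The point holds as a wording inconsistency with a consequence for participant protection. The statement in Section 6.4 that the intervention is complete at regained-capacity consent is not ensured by Sections 6.5.1, 6.5.2.2 and 6.7. As written, it would wrongly narrow the choice of a patient who regains capacity during the intervention. The size cannot be determined from the documents beyond the bounds of 0 to 40 patients.

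This rests on two assumptions: that the daily review applies from extubation, since no delay is stated, and that at least some patients score negative within about 24 hours. It is a minor point. It is worth making because the correction is cheap and concerns a stated consent rule.

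**What to change.** Reconcile Section 6.4 with Sections 6.5.1, 6.5.2.2 and 6.7. Remove the sentence, or qualify it so that it applies only when capacity returns after the intervention has ended. Add that if capacity returns earlier, the patient's decision covers the remaining intervention as well as continued data collection. Check that the regained-capacity part of Appendix C says the same, and amend it if it does not.

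Section 6.6 needs no change: patients who decline are handled there and stay in the ITT analysis, as already stated.

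The cost is an edit to the protocol text and a check of the consent form, with whatever IRB submission that requires. The downside is that a few patients may decline the remaining hours. This would lower adherence slightly, and some of them may not reach the 6-hour BiPAP threshold. The sample size and the ITT analysis are unchanged.

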6.5 Study Treatment/Interventions (Prospective Group Only)

6.5.1 Standard of Care Extubation Readiness Assessments

As standard of care, mechanically ventilated patients are reviewed daily for extubation readiness. Extubation readiness is indicated if all of the following are true: 1. The cause of respiratory failure has improved; 2. The patient can protect his or her airway; 3. Mental status is awake and alert or easily aroused; 4. Cough/secretions are appropriately managed. This standard of care extubation readiness process will occur for all patients, regardless of whether or not they are enrolled in the research study.

Once the above criteria are met, patients undergo daily spontaneous breathing trials (SBT), where the patients are observed for approximately 30-120 minutes with reduced sedation and ventilator support.

Patients that do well with minimal ventilator support during this time can generally be scheduled for extubation. All SBTs will be conducted as outlined in Appendix D.

6.5.2 Postextubation Management

6.5.2.1 Standard of Care

Patients that **do not** meet the study eligibility criteria will **not** be enrolled in the study, and will undergo postextubation management according to their physician's orders. Please note, physician orders **may** include BiPAP/HFNC, as these postextubation management strategies are routine. However, only patients that meet the all study criteria per [Section 6.3.2](#) will be included in the study.

6.5.2.2 Study Standardized, Intermittent NIV/HFNC Protocol

Patients that **do** meet all study eligibility criteria will be placed in the standardized, intermittent NIV/HFNC protocol as outlined below. For NIV, OhioHealth Grant Medical Center routinely utilizes BiPAP, a non-invasive ventilator. For HFNC, OhioHealth Grant Medical Center utilizes a heated high flow generator, an oxygen blender, and a humidifier. Please see Appendix D for BiPAP/HFNC setup, monitoring, and clinical decision making guide and Appendix E for device specification sheets.

Briefly, over the 24-hour-period following extubation, enrolled patients will receive BiPAP for 2-hour intervals (e.g., 2 hours on, 2 hours off) during the day and continuously at night. During BiPAP breaks, patients will receive heated high flow nasal cannula (HFNC) oxygen. As such, the intervention portion of this study is limited to approximately 24 hours (the 24-hour-period following extubation).

- The treating physician or advanced practice provider will order the BIPAP settings and care according to current standard methods.
- The Respiratory Therapy Team will set up, turn on and take off the BIPAP. They will also discuss the patient's care on BIPAP at the start of each shift with the RN and monitor the BIPAP approximately every 3 hours.
- The registered nurse (RN)/respiratory therapist (RT) team is responsible for the routine care they provide these patients, including assessing and monitoring the patient while they are on BIPAP for the study. They will identify, document and inform the physician and RT if problems and/or escalation of patient care occur.

6.6 End of Study Definition/Withdrawal Criteria

Patients that meet all required study eligibility criteria and for whom informed consent is obtained from the LAR will be considered enrolled into the study. A participant is considered to have completed the study after 30-day readmission data are abstracted from the medical records.

- Patients for whom informed consent is obtained but do not meet all eligibility criteria on the day of extubation will be deemed consented, not enrolled. These patients may be replaced.

- Patients who receive the study intervention but are subsequently withdrawn from the study because either they or their LAR elect to withdraw them from the study will not be replaced. Data for these patients will be included for an intention-to-treat analysis.
- Patients who receive the study intervention but for whom the intervention is discontinued or altered (due to tolerance, aversion to the BiPAP mask, or other clinical concerns) will not be replaced. Data will be included for an intention-to-treat analysis.
- It is possible that, despite a standardized order set, the intermittent treatment protocol may not be exactly 2 hours on/2 hours off during the day and that the nighttime BiPAP may not start and end at exactly the same time. Patients will be deemed to have received the protocol as directed if they receive BiPAP for at least 6 hours over a 24 hour period. All patients for whom the standardized protocol is ordered and initiated, regardless of whether or not the protocol was finished/followed, will be included in the analysis.

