2 STUDY SUMMARY

2.1 Protocol Summary Table

Protocol Title & Number	Exploratory trial to improve postextubation management for patients at risk for extubation failure IRB# 1332767
Study Short Title	GMC – [name] – Postextubation Management Pilot
Research Method	Prospective Interventional
Therapeutic Area	Pulmonary/Critical Care
Department	Intensive Care Unit, Critical Care Unit, 4 East
Study Description	This is an exploratory study designed to gather baseline information to determine the effectiveness of a standardized postextubation management protocol in a subset of patients at risk for reintubation.
Primary Endpoints	
• Proportion of patients that require reintubation within 72 hours• Association between reintubation rates and patient demographics or characteristics
Secondary Endpoints	
• Length of stay (ICU and total)• Ventilator time• In-hospital mortality• In-hospital adverse event rate• 30-day readmission rate
Prospective Cohort Study Population ^a	This study will include up to 40 mechanically ventilated, adult patients considered at-risk for re-intubation. See Section 6.3 . for detailed inclusion criteria.
Intervention(s)	
• Early NIV via BiPAP• High Flow Nasal Cannula breaks from NIV• Wean after 24 hours
Duration	Intervention Duration – Approximately 24 hours Study Duration – 3 months Participant Duration- total hospital stay, estimated at 14.1 ± 16.9 days (American Association for the Surgery of Trauma, 2011).

^a Data for this study will be compared to a historical control cohort, comprising mechanically ventilated, high-risk patients who underwent standard of care postextubation management.

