6 STUDY DESIGN

6.1 Overall Design

We propose a prospective, non-randomized exploratory study to obtain baseline data on reintubation rates for patients enrolled into a standardized postextubation management protocol compared to a historical control cohort consisting of mechanically ventilated high-risk patients that received clinician-directed, non-standardized postextubation management. We do not have current data demonstrating the specific type(s) of postextubation oxygen delivery but estimate that few patients receive combined BiPAP and HFNC. We will, however, record the types of postextubation oxygen management for the historical control cohort so that any subsequent statistical analyses can account for this potential confound.

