7.1 Statistical Analysis Plan

In general, categorical variables will be summarized with counts and percentages; and continuous variables will be summarized with means, standard deviations, medians and ranges. The two groups will be compared on categorical variables using chi-square tests, or Fisher's exact tests if the data in the contingency table have cells with expected frequency of $n < 5$. The two groups will be compared on the continuous variables using a t-test if the variable is approximately normally distributed or using a Wilcoxon rank sum test if the variable is markedly non-normally distributed. These general statistical methods will be used to compare groups on all the demographics and baseline characteristics, for the intention to treat (ITT) and per protocol (PP) populations.

Results will be considered statistically significant if the p-value is less than or equal to 0.05. SAS V9.3 or higher will be used for all summary statistics and statistical analyses.

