7.1.1 Primary Statistical Analysis Methods

Because this is a non-randomized study, it is assumed that there will be some differences between groups on the demographics and/or baseline characteristics. Therefore logistic regression modeling

techniques will be used for the primary statistical analyses. This will allow for comparison of the groups on reintubation rate while adjusting out baseline differences.

The primary analysis is comparison of the groups on reintubation rates within 72 hours on the ITT population. Potential differences between groups on demographic and baseline characteristics will be adjusted for in the model by including any statistically significant demographic and baseline characteristics as covariates in the logistic regression model.

Additional primary analyses include:

Re-intubation required (no/yes)

- a. Within 24 hours
- b. From 24-48 hours
- c. From 48-72 hours
- d. >72 hours but ≤ 7 days

The same methods used for the primary analyses will be repeated for these additional primary outcomes (within 24, 24-48, 48-72, and >72hrs) for the ITT population; and these analyses will also be repeated for the PP population (within 24, 24-48, 48-72, and >72hrs).

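### The per-protocol population is never defined; if the 6-hour BiPAP rule in Section 6.6 defines it, early reintubations drop out of the intervention group and the per-protocol 24-hour comparison is biased

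*Combined protocol and SAP*

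**What the plan says.** Section 7.1 plans baseline comparisons "for the intention to treat (ITT) and per protocol (PP) populations". Section 7.1.1 names the main analysis: "The primary analysis is comparison of the groups on reintubation rates within 72 hours on the ITT population". It then lists further primary outcomes by time window, the first being reintubation within 24 hours, and adds that "these analyses will also be repeated for the PP population (within 24, 24-48, 48-72, and >72hrs").

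Neither section says which patients form PP. Section 6.6 has the only adherence criterion: patients are "deemed to have received the protocol as directed if they receive BiPAP for at least 6 hours over a 24 hour period". It does not mention PP, and it makes no exception for a patient whose BiPAP ended because of reintubation. The same section keeps withdrawn, altered and incomplete cases for the intention-to-treat analysis.

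The schedule that determines how fast BiPAP hours accumulate is in Section 6.5.2.2: "enrolled patients will receive BiPAP for 2-hour intervals (e.g., 2 hours on, 2 hours off) during the day and continuously at night". For the historical cohort, Section 6.1 undertakes to "record the types of postextubation oxygen management for the historical control cohort", but no section says which controls PP patients are to be compared with.

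**The concern.** There are two linked problems. First, PP is a named analysis population with no membership rule for either group. With 40 intervention patients, a choice about one or two of them, made after the data are seen, can move a PP result.

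Second, the one candidate rule depends on the outcome. A patient treated exactly on schedule needs several hours to accumulate 6 hours of BiPAP. If that patient is reintubated first, the rule classes the patient as not having received the protocol, and the failure disappears from the intervention group. Every such failure falls in the 24-hour window. Controls have no BiPAP requirement, so no equivalent failures are removed from their side. Adjusting for baseline covariates does not repair a selection made on the outcome. What is at stake is the PP repeat of the within-24-hour analysis: a favourable odds ratio there could come partly or wholly from the membership rule.

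**Working it through.** The plan gives no figure for the PP set, so there is nothing to reproduce. The check has four steps.

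**1. Time needed to reach 6 hours of BiPAP** (Section 6.5.2.2 schedule, BiPAP first, extubation by day or at the start of the night):
- night begins 0 to 2 h after extubation: 6 h
- night begins 4 to 6 h after extubation: 8 h (for example, on 0–2, off 2–4, on 4–8)
- night begins 8 h or more after extubation: 10 h (on 0–2, 4–6, 8–10)

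If HFNC came first and about 10 h of daytime remained, the time would be 12 h (on 2–4, 6–8, 10–12).

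**2. Effect on the 24-hour comparison.** Assumptions: no true effect; 24-hour reintubation rate p in both groups; all controls kept; no early stoppers. The documents give no 24-hour rate and no event timing, so p and the timing are illustrative. Let h be the time at which 6 h of BiPAP is reached, L = −ln(1 − p), and k the Weibull shape (k = 1 is constant hazard).

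- Proportion reintubated before h: pre = 1 − exp(−L(h/24)^k)
- PP rate = (p − pre)/(1 − pre)
- PP odds = (p − pre)/(1 − p) and control odds = p/(1 − p), so OR = 1 − f, where f = pre/p is the share of 24-hour events removed

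For p = 0.10 and k = 1 (L = 0.1054):

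| h | pre | f | lost of 40 | PP rate v 10% | OR |
|---|---|---|---|---|---|
| 6 h | 0.0260 | 26% | 1.0 | 7.6% | 0.74 |
| 8 h | 0.0345 | 35% | 1.4 | 6.8% | 0.65 |
| 10 h | 0.0430 | 43% | 1.7 | 6.0% | 0.57 |

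The assumed rate matters little: p = 5% gives OR 0.745 (6 h) and 0.577 (10 h), and p = 15% gives 0.735 and 0.564. Timing matters more. With events clustered early (k = 0.5), the OR is 0.49 at 6 h and 0.34 at 10 h; with events clustered late (k = 2), it is 0.93 and 0.82.

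**3. Offset from early stoppers.** Suppose a share s of the intervention group stops BiPAP before 6 hours of use and none of them is reintubated. They also leave PP, as non-events, so PP rate = (p − pre)/(1 − pre − s). With p = 0.10, k = 1 and s = 10%, the OR is 0.83 (6 h) or 0.64 (10 h). The bias cancels when s = pre(1 − p)/p, which is 0.0260 × 9 = 23% at 6 h and 0.0430 × 9 = 39% at 10 h. If events cluster late (k = 2), pre is 0.0066 or 0.0181 and cancellation needs only about 6% or 16%. At k = 2, h = 6 and s = 10%, the OR is 1.05, so the sign reverses.

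**4. Later windows.** Take all patients as the denominator and the same 10% conditional rate per day. The window rates are w = 0.10 × 0.90 = 0.090 (24–48 h) and 0.10 × 0.90² = 0.081 (48–72 h), and PP rate = w/(1 − pre). For h = 6 to 10 and k = 1, the OR is 1.03 to 1.05 in both windows.

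**The case against.** **The rule is not stated to be the PP definition.** This stands, and the bias is conditional on that reading. Section 6.6 also says that everyone in whom the protocol was ordered and started will be analysed. That sentence describes ITT. If it governed PP as well, the two populations would be practically the same and the PP repeat would have no purpose.

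**The bias is not always in favour of the intervention.** A reader might infer a fixed direction, because the rule removes events only from the intervention group. The early-stopper calculation shows otherwise.

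**Twelve hours is an extreme.** At h = 12 the constant-hazard OR would be 0.49. No sentence states the order of the two therapies, but Section 2.1 lists early BiPAP and then "High Flow Nasal Cannula breaks from NIV", and Section 6.5.2.2 gives HFNC during BiPAP breaks. These make HFNC first unlikely, so the conclusion uses 6 to 10 h.

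**Larger effects or false-positive rates are not supported.** A reader might take the 19% and 23% reintubation rates cited in Section 3.2 as 24-hour rates and derive a more dramatic distortion. The protocol does not present them as 24-hour rates.

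**The shift is small beside the sampling error.** This stands. At 4/40 v 8/80, the standard error of the log OR is √(1/4 + 1/36 + 1/8 + 1/72) = 0.65, while ln 0.57 = −0.56. The shift is still systematic, and it comes from a choice that can be settled in advance.

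**The harm is confined.** The primary analysis and all secondary analyses are on ITT. It is tempting to say that the future randomised trial would be misdirected. Section 3.1 does say these data will be used to plan that trial, but nothing says the PP 24-hour result will be used for it.

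**Conclusion.** The point holds in a limited, conditional form and should be fixed. That PP is undefined for both groups is certain from the text. That the 6-hour rule would define it, and that all controls would stay in PP, are inferences. On those inferences, on-schedule patients reintubated before about 6 to 10 hours are removed because of the outcome, and the PP within-24-hour comparison is biased.

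Under an assumed 10% 24-hour rate, constant hazard, no true effect and no early stoppers, the spurious OR is about 0.74 to 0.57, or 1.0 to 1.7 of 40 patients. It could be larger or smaller with event timing, and it could be offset or reversed by early stoppers who are not reintubated. The later PP windows barely move. The documents do not support reading this as a flaw in the 72-hour ITT primary analysis, which is untouched.

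**What to change.** Amend the wording of Sections 6.6 and 7.1 before data review. The change concerns analysis only and leaves the BiPAP schedule and clinical decisions alone. The principle is that exposure cut short by reintubation or death must not count as non-adherence.

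**Preferred.** Apply the 6-hour criterion only in a landmark PP analysis: patients in both groups who are alive and still extubated at 24 hours, with outcomes counted after 24 hours. Report the within-24-hour outcome on ITT only.

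**If a PP 24-hour result is kept.** Retain every patient who started the protocol and was reintubated or died before 6 hours of BiPAP was reachable, including those whose treatment was altered for clinical deterioration. Exclude only for stopping unrelated to deterioration, such as mask aversion. A narrower rule that retained only patients with unaltered treatment would not be enough, because Section 6.6 counts other clinical concerns among the reasons for altering treatment. If a share a of the early failures followed such a change, the OR with no true effect would be 1 − a × f. With a = 50% (assumed), that is 0.87 at f = 26% and 0.79 at f = 43%.

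**In either case.** State which historical controls form the PP comparison group, and label PP as supportive because adherence is not randomised.

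**Cost.** No new patients are needed. The landmark gives no PP result for the first 24 hours. The alternative includes patients with short exposure, may look less favourable, and can keep some bias in either direction if stopping is related to risk. Confirm that BiPAP hours, the time and reason of any discontinuation, and reintubation time are collected, and for the landmark that reintubation and death times are available for controls. The data collection forms in the appendices were not among the text available for review.

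How the ordered-and-initiated sentence in Section 6.6 fits with the enrolment definition is a separate ITT question and adds no weight here.
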